## **Materials and Methods**

This in vivo study was a prospective, single-center; single blinded, parallel, and randomized clinical trial. The study protocol was approved by the Ethics Committee of Cukurova University Faculty of Medicine, Adana, Turkey (2019/12197-91).

## **Patient Selection**

One hundred patients with a noncontributory medical history presented to the Department of Endodontics of the University of Cukurova Faculty of Dentistry between October 2019 and February 2020 were selected according to inclusion and exclusion criteria. All selected teeth were single-rooted, maxillary and mandibular incisors, canines or premolars that were asymptomatic (no preoperative pain, swelling or acute endodontic or periodontal abscess). All pulps were nonvital and did not respond to cold testing. All patients were aged between 18 and 65 years, had no systemic diseases or allergies to local anaesthetic agents, had not previously received any endodontic treatment and had no radiographic evidence of periapical bone loss. Pregnant and breast-feeding women and patients taking analgesic, anti-inflammatory or antibiotic medications during the 7 days prior to the beginning of treatment were also excluded. All patients were informed that they were to be included in a clinical trial and their consent was obtained.

Based on the study of Verma et al., a change in PAI score of 0.50 units and above is found to be clinically significant, and at least 42 patients per group should be included at 90%

power and 5% margin of error, assuming the standard deviation of the change is 1.0. Given the possibility of dropouts throughout the study, it was planned to take 20% more and to conduct the study on 50 patients per group.

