#### **Randomization of Groups**

Based on the study of Verma et al., a change in PAI score of 0.50 units and above is found to be clinically significant, and at least 42 patients per group should be included at 90% power and 5% margin of error, assuming the standard deviation of the change is 1.0. Given the possibility of dropouts throughout the study, it was planned to take 20% more and to conduct the study on 50 patients per group.

The teeth included in the study were divided into two treatment groups (Control and MTAD group) by using a randomized block design of 10 patients per block. These randomization blocks were prepared on the computer by a biostatistician. During treatment, the dental practitioner used the irrigation solution according to the order defined in the randomization block. The patients were uninformed of which solution was used; in this regard our study was a single-blind clinical trial.

04/09/2019

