**Statistical Analysis**

The data were statistically analysed using the IBM SPSS Statistics Version 20.0 program (IBM, Armonk, NY, USA). Gender distribution according to groups was evaluated with Chi-square analysis and age distribution t-test. The Mann-Whitney U test was used to compare the differences (pre-treatment, post-treatment change) between the groups' pre-treatment and 24-month follow-up radiographs. The change in PAI scores for each group from baseline to the end of follow-up was evaluated with the Wilcoxon test. The Chi-Square test was used to compare bilateral variables (teeth with a PAI  $\leq 2$  scores 'healthy', teeth with a PAI  $\geq 3$  score 'failure') between two groups. In all tests, the statistical significance level was set at 0.05.

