**Results:**

In the MTAD group, 2 patients were excluded from the study due to health problems and 1 patient was excluded because of pregnancy. A total of 97 patients, 64 females and 33 males (47 MTAD, 50 Control) with apical periodontitis, were included in this study. After a 24-month follow-up, 25 of the 97 patients (15 Control and 10 MTAD) were excluded from the study because of not to attend follow-up appointments. Pre-treatment and 24-month follow-up radiographs of a total of 72 teeth, 37 in the MTAD group and 35 in the Control group, were examined and evaluated according to the PAI score.

Age and gender distribution were compatible between the groups, and no statistically significant difference was found in terms of gender (Chi-Square Test) and age (t-test) ( $P > 0.05$ ). Initial PAI scores were consistent in the teeth with periapical lesions of the patients in

the two groups, but there was no statistically significant difference between them. There was no significant difference in baseline and follow-up scores between groups ( $p=0.744$ ,  $p=0.469$  respectively). No change was observed in the PAI score of 3 patients (8.6%) in the Control group and 4 patients (10.8%) in the MTAD group. There was no statistically significant difference between the groups' post follow-up PAI scores ( $p= .551$ ).

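### The 50 enrolled per group keep the stated minimum of 42 only up to a 16% loss; 35 and 37 were analysed, so the stated 90% power does not apply to the null result

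*Combined protocol and SAP*

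**What the plan says.** The sample size paragraph appears twice in the Combined protocol and SAP, under Patient Selection and again under Randomization of Groups. Its inputs are a difference ("a change in PAI score of 0.50 units and above is found to be clinically significant") and a spread ("assuming the standard deviation of the change is 1.0"). From these it concludes "at least 42 patients per group should be included at 90% power and 5% margin of error". Because patients may drop out, "it was planned to take 20% more and to conduct the study on 50 patients per group". Neither section states an expected dropout rate.

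Statistical Analysis sets the level for all tests ("In all tests, the statistical significance level was set at 0.05") without saying whether it is one- or two-sided. It compares the change in PAI score between the groups with the Mann-Whitney U test.

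Results reports three exclusions in MTAD and 25 patients who missed follow-up, 15 in Control and 10 in MTAD. That leaves "37 in the MTAD group and 35 in the Control group". The between-group comparisons there are non-significant (p = 0.744, 0.469 and .551). Radiographic and Clinical Evaluation attributes many missed appointments to the pandemic.

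**The concern.** The 20% margin is introduced for dropouts, and no other percentage is given, so a reader will probably take it as cover for a 20% loss. It is not: it covers 16%. The numbers analysed then fall below the plan's own minimum in both groups, and nothing in the document says so.

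What is at stake is the reading of a null result. Someone who sees non-significant group comparisons next to a stated 90% power will conclude that a difference of 0.50 PAI units was very likely to have been detected had it existed. The trial did not have that power at the numbers it analysed.

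**Working it through.** **Inputs.** Minimum 42 per group, power 90%, difference 0.50, SD 1.0, 50 enrolled per group (Patient Selection; Randomization of Groups). Significance level 0.05 (Statistical Analysis), taken as two-sided, which is an assumption. Exclusions, losses and numbers analysed from Results.

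**1. The plan's own figures.**
- Allowance: 42 × 1.20 = 50.4, stated as 50. This reproduces, apart from rounding down.
- Base figure: the one-group (within-group change) normal formula gives n = (1.960 + 1.282)² × 1.0² / 0.50² = 42.03, which matches 42. The document does not name its formula, so this is inferred. A one-sided version gives 34.3, which does not match.

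**2. What 50 per group covers.**
- Largest loss that keeps 42: 1 − 42/50 = 16%, or 8 patients.
- After a 20% loss: 50 × 0.80 = 40, two short.

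**3. What happened.**
- Control: 50 − 15 = 35; loss 15/50 = 30%.
- MTAD: 50 − 3 − 10 = 37; loss 13/50 = 26%.
- Both are below 42.

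**4. Power on the one-group calculation.** Power = Φ(0.50 × √n / 1.0 − 1.960).

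| n | 0.50√n − 1.960 | Power |
|---|---|---|
| 42 | 1.280 | 90.0% |
| 40 | 1.202 | 88.5% |
| 37 | 1.081 | 86.0% |
| 35 | 0.998 | 84.1% |

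**5. Power for the between-group comparison.** Two-sample t-test, difference 0.50, SD 1.0, two-sided 0.05, used as an approximation to the Mann-Whitney test.

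| Numbers | Power |
|---|---|
| 50 v 50 | 70% |
| 42 v 42 | 62% |
| 35 v 37 | 55% |

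Difference detectable with 90% power at 35 v 37: by the normal formula, 3.242 × √(1/35 + 1/37) = 3.242 × 0.2358 = 0.764; on the t distribution, 0.775. So about 0.77 PAI units, against the 0.50 planned.

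**6. Splitting the fall.** From 90% to 55% is 35 points. Of these, 90 − 62 = 28 are present with the full 42 per group and come from using a one-group size for a two-group comparison. The remaining 62 − 55 = 7 come from analysing 35 and 37 instead of 42.

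**The case against.** A reader might infer that the plan made an arithmetic error by multiplying 42 by 1.2 when it should have divided by 0.8, giving 42/0.8 = 52.5, or 53. The documents do not support this. They describe a 20% addition to enrolment, and that is what was done. They never state a 20% expected loss, and dividing by 0.8 would be right only if they had.

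A reader might also infer that the allowance caused the shortfall. It did not. At the losses seen, 53 per group would have left 53 × 0.70 = 37.1 and 53 × 0.74 = 39.2, still below 42. The sample size section carries a date of September 2019 and recruitment ran from October 2019 to February 2020. The document blames the pandemic for many missed visits.

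Two further objections are fair. The effect of the allowance alone is small: 40 against 42 evaluable, or 88.5% against 90% power on the one-group calculation. And most of the drop to 55% belongs to the separate question of how 42 was derived, so it should not be counted against the dropout allowance.

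It is also true that Results reports the losses and the numbers analysed openly by group. What the document lacks is the link back: 35 and 37 are fewer than the stated minimum, and the 90% figure stands without qualification in both sections.

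**Conclusion.** The point holds as a mismatch between a stated property and what the trial delivered, not as a proven formula error. Fifty per group protects 42 only up to a 16% loss. With losses of 30% and 26%, the analysed 35 and 37 do not meet the stated minimum, and the 90% power does not apply to the null result.

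On the calculation that reproduces 42, the loss of power is modest, to about 84% and 86%. For the comparison between groups, power is about 55%, of which only about 7 of the 35 points lost are due to the smaller numbers.

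These figures assume a difference of 0.50, SD 1.0 and two-sided 0.05. The one-group formula is inferred from its match to 42, and the t-test stands in for the Mann-Whitney test on a five-category score.

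**What to change.** In Patient Selection and Randomization of Groups, add that 50 per group keeps 42 evaluable for a loss of up to 16%. Leave the original planning figures visible as the planning rationale.

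Beside the results, add a limitation along these lines: the numbers analysed, 35 and 37, are below the planned 42, so the 90% power does not apply to the comparisons reported; for a between-group difference of 0.50 units with SD 1.0 at two-sided 0.05, power is about 55%, and about 0.77 PAI units would be detectable with 90% power (t approximation to the Mann-Whitney test). Say also that power would be only about 62% with 42 per group, so most of the gap comes from the basis of the original size, not from dropout. The one-group figures of about 84% and 86% can be given alongside, marked as resting on an inferred formula.

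Do not insert 53 as a corrected sample size. The plan states no 20% loss, and 53 would treat 42 as a sound base for a two-group comparison.

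The cost is a few sentences and a less favourable power statement. No further recruitment and no change to the analysis follow.

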### **Root Canal Procedure**

The initial periapical radiographs of the patients were taken with the digital imaging system Digora Optime (Soredex, Tuusula, Finland) by long-cone paralleling technique with a film holder (Endo Rh plus; Indusbello, Londrina, PR, Brazil), the vitality of the pulp was evaluated by an electronic vitalometer (Analytic Technology Corp., Redmond, WA, USA) and confirmed by the absence of bleeding from the endodontic access cavity.

For both maxillary and mandibular teeth, local infiltration anaesthesia was achieved using 2 mL articaine hydrochloride with 1:200 000 adrenaline (Maxicaine; VEM Ilac, Istanbul, Turkey). Endodontic access preparations were performed using diamond round burs. After the canals were visible, patency was checked with a K-file (VDW GmbH, Munich, Germany), and a dental dam was placed to isolate the tooth. The working length (WL) was determined with an electronic apex locator (Raypex 6, VDW) and accepted when all 3 green bars were reached. In addition, the canal length was confirmed by a periapical radiograph, and the apex locator was accepted as correct in situations where the two did not match. Root canal instrumentation was performed using the Reciproc Blue (VDW, Munich) #50/0.5 file. During instrumentation of the root canals, irrigation was applied with 10 mL 2.5% NaOCl using side-vented needles (NaviTips, 30 gauge; Ultradent, South Jordan, UT, USA). The final irrigation in Control group was applied with 5 ml of 17% EDTA solution and 5 ml of distilled water. In the MTAD group, final irrigation was done with 5 mL of MTAD and 5 mL of distilled water. Side-vented needles were placed 1 mm shorter than the working length, and 5 ml of solution was given in 2 minutes. The root canals were dried with sterile paper points and were filled with cold lateral condensation technique using AH Plus root canal sealer (Dentsply Maillefer,

Cologne, Germany) and gutta percha (President Dental, Duisburg, Germany). Then the cavity entry was restored with composite (Solarex, GC Corporation, Tokyo, Japan) and radiography was taken.

### **Radiographic and Clinical Evaluation**

Patients were invited to follow-up sessions at 6, 12, 18, and 24 months and were radiographically and clinically assessed. Many patients missed their follow-up appointments due to the covid 19 pandemic. The follow-up radiographs performed by long-cone paralleling technique with a film holder. The pre-treatment and 24-month follow-up radiographs of teeth, were prepared as a Power Point presentation (Microsoft ® Corporation, Redmond, WA) and the change in periapical radiolucency was assessed according to PAI scores of five categories; 1. Normal apical periodontium 2. Small changes in bone structures 3. Change in bone structure with mineral loss 4. Periodontitis with well-defined radiolucent area 5. Severe periodontitis with exacerbating features. Teeth with a  $PAI \leq 2$  score and clinically asymptomatic were considered 'healthy' in the radiographic evaluation, while teeth with a  $PAI \geq 3$  and/or clinically symptomatic were considered 'failure'.

#### **Randomization of Groups**

Based on the study of Verma et al., a change in PAI score of 0.50 units and above is found to be clinically significant, and at least 42 patients per group should be included at 90% power and 5% margin of error, assuming the standard deviation of the change is 1.0. Given the possibility of dropouts throughout the study, it was planned to take 20% more and to conduct the study on 50 patients per group.

The teeth included in the study were divided into two treatment groups (Control and MTAD group) by using a randomized block design of 10 patients per block. These randomization blocks were prepared on the computer by a biostatistician. During treatment, the dental practitioner used the irrigation solution according to the order defined in the randomization block. The patients were uninformed of which solution was used; in this regard our study was a single-blind clinical trial.

04/09/2019

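### The 42 per group fits a within-group change; on the stated inputs the MTAD-versus-control comparison has about 62% power at 42 and 70% at 50 per group, not 90%

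*Combined protocol and SAP*

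**What the plan says.** The sample size paragraph of the combined protocol and SAP appears twice, under Patient Selection and under Randomization of Groups. It takes a PAI change of 0.50 units as clinically significant, assumes a standard deviation of the change of 1.0, and concludes that "at least 42 patients per group should be included at 90% power and 5% margin of error". It then adds 20% for dropout and sets 50 per group. It names no test, does not say whether the 0.50 is a change within a group or a difference between groups, and does not say whether the 5% is one- or two-sided.

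Materials and Methods describes a "single blinded, parallel, and randomized clinical trial". Statistical Analysis plans two tests of change in PAI:

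- Between groups: "The Mann-Whitney U test was used to compare the differences (pre-treatment, post-treatment change"), applied to the pre-treatment and 24-month radiographs.
- Within groups: "The change in PAI scores for each group from baseline to the end of follow-up was evaluated with the Wilcoxon test".

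Results reports the numbers analysed as "37 in the MTAD group and 35 in the Control group".

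**The concern.** In a parallel two-arm trial, a patient number per group at 90% power will be read as power to detect a difference between the arms. That is the comparison randomization protects and the one that addresses the effect of MTAD. A pre-to-post change within one arm does not use the randomization and cannot show whether MTAD adds anything to the control irrigation.

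The stated number looks too small for the between-arm comparison by a factor of two. At 90% power, the chance of missing a true 0.50-unit difference would be 10%. If actual power is 62% to 70%, that chance is 38% to 30%.

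This affects how the outcome is read. Results states "There was no significant difference in baseline and follow-up scores between groups", with p = 0.744 and p = 0.469, and gives p = .551 for a further comparison of post-follow-up scores. It gives the number of patients with unchanged PAI in each arm, but no between-arm difference and no confidence interval. The weight a reader gives to these null findings therefore depends on the stated power.

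**Working it through.** **Inputs** (sample size paragraph, unless noted)

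- Difference: 0.50 PAI units
- SD: 1.0, stated to be the SD of the change, so no further reduction for baseline correlation applies
- Power: 90%, z = 1.2816
- Error rate: 5% (Statistical Analysis also gives 0.05). Taken as two-sided, z = 1.96; this is an assumption, and the one-sided case is shown below
- Allocation: 1:1

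**Step 1. Reproduce the stated 42.** One-sample formula for the mean change in a single group:

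n = (1.96 + 1.2816)² × (1.0/0.50)² = 10.507 × 4 = 42.03

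This matches 42. One-sample t-test power at n = 42 is 88.6%. The dropout step is 42 × 1.2 = 50.4, taken as 50.

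**Step 2. Same inputs, two independent groups.**

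n per group = 2 × (1.96 + 1.2816)² × (1.0/0.50)² = 2 × 42.03 = 84.06

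Rounded up this is 85. The t test gives power of 0.8999 at 85 per group and 0.903 at 86, so it needs 86.

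**Step 3. Between-group power at the numbers in the document.** The standard error of the difference is 1.0 × √(1/n₁ + 1/n₂). Power is from the two-sided t test for a difference of 0.50. The half-width is the t quantile times the standard error.

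| Patients per group | Standard error | Power for 0.50 | Difference with 90% power | Expected 95% CI half-width |
|---|---|---|---|---|
| 42 / 42 (stated minimum) | 0.218 | 62.0% | 0.716 | 0.434 |
| 50 / 50 (planned) | 0.200 | 69.7% | 0.655 | 0.397 |
| 35 / 37 (analysed) | 0.236 | 55.2% | 0.775 | 0.470 |

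The normal approximation gives 63.0% at 42 and 70.5% at 50. The 35/37 row reflects loss to follow-up, which Radiographic and Clinical Evaluation attributes in part to the pandemic ("Many patients missed their follow-up appointments due to the covid 19 pandemic"). That further loss is not part of the planning error.

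At 35/37 and SD 1.0, an interval excludes 0.50 in both directions only if the observed difference lies within 0.50 − 0.470 = 0.030 of zero. A larger observed difference would exclude it in one direction only.

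**Step 4. Do other assumptions restore 90%?**

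| Assumption | Power at 42 per group | Power at 50 per group |
|---|---|---|
| One-sided 5%, t test | 73.5% | 79.9% |
| Mann-Whitney, efficiency 3/π under normality, two-sided | about 60% | about 68% |
| SD 0.7, two-sided t | 89.9% | 94.3% |
| SD 0.8, two-sided t | 80.8% | 87.2% |
| SD 0.9, two-sided t | 71.1% | 78.5% |
| SD 1.2, two-sided t | 47.1% | 54.1% |

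Reaching 90% at 42 per group requires an SD of about 0.70. The document states 1.0.

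**The case against.** The strongest reply is that the paragraph contains no wrong number. It speaks of a change and of the SD of the change, and it never says that the 90% refers to MTAD against control. On those terms 42 is right for the within-group Wilcoxon comparison, which the plan does include. This stands as far as it goes: the fault is that the number does not support the comparison a reader will attach to it. But on this reading the randomized comparison has no stated power at all, so a correction is needed either way.

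The origin of 42 is also inferred. Reading 84 as a total for both groups and halving it would give 42 as well, and the document cannot separate the two explanations. Neither changes the between-group power.

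Sidedness is not stated, and the planned between-group test is Mann-Whitney on a five-category score, so the t-test figures are approximations. Both points are fair. One-sided testing narrows the gap without closing it, and the Mann-Whitney adjustment lowers power slightly.

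Finally, the trial is complete, its tests remain valid, and Results neither claims equivalence nor cites the 90%. The reported p-values quoted above also concern scores, not change. The harm is therefore one of interpretation: the p-values are not wrong, but the stated power makes a null result look more informative than it is.

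**Conclusion.** The concern holds. On the plan's own inputs, 42 per group gives about 90% power only for a within-group change of 0.50. For the between-arm comparison of change, power is about 62% at 42 per group and 70% at 50, a shortfall of 28 and 20 percentage points. About twice the stated minimum, 85 to 86 per group, would have been needed before any dropout allowance.

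This rests on reading 1.0 as the SD of each patient's change, on a two-sided 5% level, and on the t test as an approximation to the planned Mann-Whitney test. One-sided testing does not restore 90% at either size. A smaller SD would: about 0.70 at 42 per group, which is not what the plan assumes. The finding does not show that MTAD and control differ. It shows that the design could miss a 0.50-unit difference much more often than stated.

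**What to change.** Add a dated correction or stated limitation that covers the paragraph in both places and leaves the original text visible. It should say that:

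- 42 per group gives about 90% power only for a within-group change of 0.50 with SD 1.0;
- between-group power for 0.50 is about 62% at 42 and 70% at 50 per group, with the sidedness and the test stated;
- 42 per group has 90% between-group power for a difference of about 0.72.

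With the results, report the between-arm difference in PAI change and its 95% confidence interval, and name the estimator. A difference in mean change is on the same scale as the 0.50 and the SD of 1.0. Let that interval decide whether a 0.50-unit difference is excluded, and do not read non-significance alone as no difference.

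The cost is a short note and one interval from data already collected. No additional patients are required. The stated power becomes less favourable.

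### No allocation concealment or point of disclosure is described, so the unmasked operator could know the arm before eligibility is settled and during the shared canal preparation

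*Combined protocol and SAP*

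**What the plan says.** The Randomization of Groups section allocates teeth to Control or MTAD "by using a randomized block design of 10 patients per block". On who made the list: "These randomization blocks were prepared on the computer by a biostatistician". On who applied it: "During treatment, the dental practitioner used the irrigation solution according to the order defined in the randomization block". On masking: "The patients were uninformed of which solution was used; in this regard our study was a single-blind clinical trial".

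The file then prints 14 blocks of 10 in full under Randomization Blocks, followed by the code (1 is Control, 2 is MTAD). The randomisation page carries the date 04/09/2019. Patients presented "between October 2019 and February 2020 were selected according to inclusion and exclusion criteria", so the list predates enrolment whichever way the day and month are read.

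Two other sections bear on timing:

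- **Eligibility.** Patient Selection requires a nonvital pulp: "All pulps were nonvital and did not respond to cold testing". Root Canal Procedure adds an electronic vitality test, with the finding "confirmed by the absence of bleeding from the endodontic access cavity".
- **Common treatment.** Root Canal Procedure gives both arms the same access, working-length method, file and irrigant: "During instrumentation of the root canals, irrigation was applied with 10 mL 2.5% NaOCl using side-vented needles". The arms part only at the final irrigation, with EDTA in Control and MTAD in the other arm.

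**The concern.** Randomisation protects a comparison only if the next assignment is unknown to the person who decides whether a tooth enters the trial. Here the treating dentist follows the sequence, is not masked, and makes the last eligibility check during the treatment visit. Nothing in the plan puts a barrier between that person and the next assignment.

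Two routes to bias stay open:

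1. **Selection.** A dentist who knows the arm could accept, defer or reject a tooth in light of it.
2. **Unequal background treatment.** Access, working length, instrumentation and NaOCl irrigation are meant to be the same in both arms. An operator who already knows the arm could deliver them differently, even without intent.

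Either would carry into every between-arm test in the Statistical Analysis section, and no analysis of the collected data could fully remove it. The point is separate from whether the radiograph readers were masked. It concerns who enters each arm and how the common steps are carried out.

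**Working it through.** **Step 1. Order of events against what the plan protects.**

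| Event | Section | Is the operator's ignorance of the arm required? |
|---|---|---|
| Cold test, vitality test | Patient Selection; Root Canal Procedure | Not stated |
| Access opened, nonvitality confirmed | Root Canal Procedure | Not stated |
| Working length, instrumentation, NaOCl | Root Canal Procedure | Not stated |
| Final irrigation (arms diverge) | Root Canal Procedure | Arm must be known here |

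The arm is needed only in the last row. The plan does not restrict disclosure in any earlier row, so it permits knowledge of the arm at all of them. It does not establish that the operator had that knowledge.

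**Step 2. Does the printed list match the stated design?** Yes. Each of the 14 rows has 10 entries, five of each code, giving 14 × 10 = 140 assignments. The first ten rows cover the planned 100 patients.

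**Step 3. What do fixed blocks reveal if the list itself is hidden?** Assume that the operator knows the block size and the past assignments, which an unmasked operator would. All counts use the first ten blocks.

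- *Certain assignments.* Once one arm has used its five places, the rest of the block is determined. By block: 1 + 1 + 2 + 1 + 1 + 1 + 1 + 2 + 3 + 1 = 14 of 100.
- *Best guessing.* Guess the arm with more places left, and score 0.5 when they are level. In a 5:5 block the score is 5 + T/2, where T is the number of assignments made from a level position. By block, T is 4, 3, 1, 4, 2, 3, 2, 4, 1, 4, which totals 28. The score is 50 + 28/2 = 64 of 100, against 50 by chance.

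**Step 4. Is that unusual?** For a balanced block of 2m:

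- expected certain assignments = 2m/(m + 1). With m = 5 this is 10/6 = 1.67 per block, or 16.7 per 100;
- expected correct guesses = m + ½[4^m / C(2m, m) − 1]. With m = 5 this is 5 + ½(1024/252 − 1) = 6.53 per block, or 65.3 per 100.

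The same guessing formula gives 70.8% for blocks of 4 and 68.3% for blocks of 6. The printed list is slightly less predictable than an average list in blocks of 10, and shorter fixed blocks would be worse. Block size is therefore not the main weakness. The missing concealment step is.

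**Step 5. Can the bias be sized?** No. That would need the frequency with which the arm was known early, what the operator did with that knowledge, and its effect on PAI. The documents give none of these.

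**The case against.** The strongest reply is that the plan is silent on concealment, and silence is not evidence of an open list.

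- **Custody and timing.** No section says that the dentist held the list or the code. The wording on use during treatment fits a look-up at the final rinse as well as an open sheet. The printed list and key sit in a file that also contains the Results, so they show that a list existed, not who could see it. This stands. A reader might infer that all 100 assignments were known in advance; the documents do not support that.
- **Eligibility.** The randomisation text speaks of teeth already included being divided, and nonvitality is first judged by cold and electronic testing, so the bleeding check only confirms it. The Results report 50 Control and 47 + 3 = 50 MTAD patients, as ten complete blocks would give, and no exclusion after access. This narrows the room for selection but does not close it: a tooth set aside before being counted would leave no trace in these totals.
- **Standardisation.** Only single-rooted teeth are eligible. The file, the NaOCl volume and strength, the needle type and the rule for conflicting length readings are fixed. This limits operator discretion without removing it.
- **Baseline similarity.** Baseline PAI scores did not differ (p = 0.744), so nothing points to imbalance in lesion severity. The Results report no comparison of canal difficulty or preparation quality, so the test cannot settle the question.

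The opposite inference also fails. All three early exclusions were in MTAD, which might look like steering. The two-sided probability that all three fall in one arm is 2 × (50 × 49 × 48)/(100 × 99 × 98) = 0.24, and the stated reasons are health problems and pregnancy. That is not evidence of selection.

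**Conclusion.** The concern holds as a gap in the plan, not as a finding about what happened. The unmasked operator follows the block order, with no described concealment and no point of disclosure. The operator could therefore know the arm before nonvitality is confirmed and during the shared preparation.

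The size and direction of any bias cannot be computed. The only calculable quantity is the residual predictability of the fixed blocks with the list hidden: 14 certain assignments and 64 expected correct guesses in the first 100. It assumes that the operator knew the block size and tracked past assignments. It is ordinary for blocks of 10 and secondary.

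The conclusion rests on the text available, in which the randomisation section gives no such safeguard. If assignments were in fact concealed, one sentence saying so would largely answer the point. It should be fixed or clarified, but it does not by itself invalidate the comparison.

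**What to change.** **In the Randomization of Groups section**, replace the sentence on the practitioner following the block order with a procedure along these lines:

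- The biostatistician, or another person not treating the patient, holds the list and the code.
- Assignments are placed in sequentially numbered, opaque, sealed envelopes.
- The patient is entered in the log once eligibility, including nonvitality at access, is confirmed.
- The envelope is opened only after instrumentation and NaOCl irrigation are complete, immediately before the final irrigation.

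Randomly varied block sizes are optional and matter less than the steps above.

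**Cost.** Envelopes and a short paragraph, with no extra patients, staff or clinical procedures and no change in sample size. The small downside is that both rinses must be at hand until the envelope is opened.

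**For the trial already run**, new wording cannot change how patients were allocated. The report should:

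1. state whether, how and until when allocation was concealed, and who held the list;
2. compare the dated treatment log with the printed sequence and report any departure;
3. qualify the between-arm conclusion if allocation was not concealed.

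The authors should not be asked to declare that allocation was unconcealed, because that may be untrue. The cost is one log check and a few sentences.
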